6.2.1 Sample size calculations for immunogenicity

The main goals of this trial regarding immunogenicity outcomes involve assessing the ability of FP-conjugate and Trimer 4571 vaccines alone or co-administration to elicit antibody binding FP and envelop trimer antigens and mapping FP-specific serum neutralizing activity induced by the prime vaccines regimens in Groups 5-8 and prime boost vaccines regimens in Groups 7-8. No adjustment for multiple comparisons will be made for the use of multiple assays. The precision with which the true response rate can be estimated from the observed data depends on the true underlying response rate and the sample size. Two-sided 95% CIs for the response rate based on observing a particular rate of responses in the vaccinees is shown in [Table 6-3](#). Calculations are done using the score test method (52). The sample size of n = 13 (Groups 5-6) and n=9 for each of Groups 7 and 8 will be used to evaluate the immunogenicity post the 1st vaccination induced by the vaccination; the sample sizes of n=4, 5 for Groups 7-8 will be used to evaluate the immunogenicity post the 2nd vaccination.

Table 6-3 Two-sided 95% confidence intervals for the true response rate based on observing a particular rate of responses in the vaccinees (n =4, 5, 9, 13)

No. of responses	Observed response rate (%)	95% Confidence interval
2/4	50	[15, 85]
4/4	100	[51, 100]
2/5	40	[11.8, 76.9]
4/5	80	[37.6, 96.4]
3/9	33.3	[12.1, 64.6]
6/9	66.7	[35.4, 87.9]
9/9	100	[70.1, 100]
3/13	23.1	[8.2, 50.3]
6/13	46.2	[23.2, 70.9]
9/13	69.2	[42.4, 87.3]

As shown in [Table 6-4](#), there is limited power for a formal comparison of immunogenicity response rates between Group 7 (n=9) and Group 8 (n=9). For either 80% or 90% power, the sizes of differences that the trial is powered to detect are fairly large. These calculations use a Fisher exact 2-sided test with a type I error rate of 0.05.

Table 6-4 Power for comparison of response rates between 2 arms (n1 = 9, n2 = 9)

True response rate Arm 1 (%)	Minimum true response rate in Arm 2 in order to detect a difference	
	80% power	90% power
10	83	91
20	92	99
30	99	

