For quantitative assay data (eg, the vaccine-induced serum neutralizing antibody [nAb] as measured by the TZM-bl assay, HIV-specific serum IgG binding magnitude, breadth, and avidity to cross-clade panels of gp120 and V1V2 and to V3, CD4i, gp41 and gp41 immunodominant region [IDR] as assessed by the binding antibody multiplex assay [BAMA] or CD4+ T-cell responses to Gag and Env as assessed by ICS), graphical and tabular summaries of the distributions by antigen, treatment arm, and timepoint will be made. For all primary and secondary immunogenicity endpoints, box plots and plots of estimated reverse cumulative distribution curves will be used for graphical display of all of the study arms. Typically, the results will be shown for each vaccine arm.

The difference between arms at a specific timepoint will be tested with a nonparametric Wilcoxon rank sum test if the data are not normally distributed and with a 2-sample t-test if the data appear to be normally distributed. To test for differences among all vaccine arms, first a Kruskal-Wallis rank test or an F-test (depending on the normality assumption) will be used to test for overall differences. Secondly, if the overall test is significant at the 2-sided 0.05 level, then individual tests comparing between vaccine arms will be done. If rank-based tests are used, then the tests will be inverted to construct Hodges-Lehmann point estimates and 2-sided $(1-0.05/\# \text{ of comparisons}) \times 100\%$ CIs about the differences in location centers of the number of comparisons between vaccine arms. If rank-based tests are used, then the tests will be inverted to construct Hodges-Lehmann point estimates and 2-sided $(1-0.05/\# \text{ of comparisons}) \times 100\%$ CIs about the differences in location centers of the number of comparisons between vaccine arms. When all pair-wise comparisons between the multiple vaccine arms are of interest, the Tukey procedure (56) will be used. If only specific comparisons

between pairs of the multiple vaccine arms are of interest, the Holm-Bonferroni procedure will be used. An appropriate data transformation (eg, log10 transformation) may be applied to better satisfy assumptions of symmetry and homoscedasticity (constant variance). Significance of the differences between pairs will be evaluated using 2 procedures, first based on whether the simultaneous 95% CIs exclude zero and secondly, based on whether the nominal (unadjusted) 95% CIs exclude zero.

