6.5.4.4 Secondary analyses of neutralization magnitude-breadth curves

Superiority comparisons of vaccine regimens passing the tier-2 screen

For the set of vaccine regimens that passed the tier-2 screen, an F-test will be performed for whether any of the mean AUC-MBs differ. If this test is not significant ($p\text{-value} > 0.05$), then the conclusion will be that there were no significant differences in mean AUC-MBs among the vaccine regimens that advanced. If the F-test is significant, then simultaneous 95% CIs about the mean-differences in AUC-MBs will be reported. These CIs are computed as the estimated mean-difference plus or minus $t_{N-m,025}$ multiplied by the square-root of $S^2 (1/n_i + 1/n_j)$, where $t_{N-m,025}$ is the 97.5th percentile of a t-distribution with $N - m$ degrees of freedom, where N is the total number of vaccine recipients evaluated (summing over the advanced vaccine regimens) and m is the number of advanced vaccine regimens. In addition, S^2 is an estimate of the common sample variance of the AUC-MB, whereas n_i and n_j are the sample sizes of evaluable participants

for vaccine regimens i and j being compared. Following Fisher's least significant difference procedure, the pairs of vaccine regimens with this CI, excluding zero, are deemed to have a significant difference. Nominal (unadjusted) 95% CIs about pairs of vaccine arms will also be reported.

Omnibus comparison of magnitude-breadth distributions

The analyses of magnitude-breadth described above are based on the endpoint area-under-the-curve, which is interpreted as the average \log_{10} half-maximal inhibitory concentration (IC50) to the set of isolates in the test panel. Use of this endpoint is maximally statistically powerful if 1 vaccine arm has greater magnitude and breadth than the comparator vaccine arm, but may miss an effect wherein 1 vaccine arm has greater magnitude and the comparator vaccine arm has greater breadth. Therefore, a secondary analysis may compare the distribution of magnitude-breadth curves among vaccine arms using the test statistic $\max|B_d^G|$ from Huang, et al (63), which is designed to detect general differences in magnitude-breadth curve distributions.

Selecting the best vaccine regimen among those passing the tier-2 screen

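### Protocol 6.5.4.4: the AUC-MB intervals called simultaneous 95% are unadjusted LSD intervals (joint coverage about 88% with three regimens), and the optional best-regimen rule names a placebo group the trial does not have

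*Protocol*

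**What the plan says.** Protocol Section 6.5.4.4 covers regimens that pass the tier-2 screen of Section 6.5.4.3. It starts with an F-test on mean AUC-MB and continues: "If the F-test is significant, then simultaneous 95% CIs about the mean-differences in AUC-MBs will be reported". Each interval is the estimated mean difference plus or minus a critical value times the square root of S²(1/n_i + 1/n_j). The critical value "is the 97.5th percentile of a t-distribution with" N − m degrees of freedom, where N is the number of evaluated recipients and m the number of regimens that advanced. Decisions follow Fisher's "least significant difference procedure, the pairs of vaccine regimens with this CI, excluding zero, are deemed to have a significant difference". The section then adds: "Nominal (unadjusted) 95% CIs about pairs of vaccine arms will also be reported".

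Two neighbouring sections show what the protocol means by simultaneous. Section 6.5.4.3 uses the word for three Dunnett intervals with joint coverage of at least 95%. Section 6.5.4.1 judges pairs by two separate procedures, "first based on whether the simultaneous 95% CIs exclude zero and secondly, based on whether the nominal (unadjusted) 95% CIs exclude zero", and states: "When all pair-wise comparisons between the multiple vaccine arms are of interest, the Tukey procedure (56) will be used".

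Later in Section 6.5.4.4, an optional analysis picks the best regimen by the largest max|B| statistic against pooled placebo recipients. Section 9.2.1 says that the protocol administers no placebo. The screen in Section 6.5.4.3 uses pooled baseline samples from Groups 6-8 as its reference.

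**The concern.** With three regimens there are three pairwise intervals. A set called simultaneous 95% should contain all three true differences 95% of the time. The formula gives each interval 95% coverage separately, so the joint figure must be lower. A reader of the report would be told of a joint confidence that the intervals do not have. The contrast drawn in Section 6.5.4.1 between simultaneous and nominal intervals also disappears, because both sets in Section 6.5.4.4 are unadjusted.

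The comparator in the max|B| rule is a separate defect of the same kind. The text names a group that does not exist, so it does not say what to compute. If the comparator is chosen after the data are seen, there is avoidable discretion over which regimen is called best.

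**Working it through.** **Inputs.** Protocol Section 6.2.1, after the first vaccination: "The sample size of n = 13 (Groups 5-6) and n=9 for each of Groups 7 and 8 will be used". Group 5 has 3 participants (Table 1-1), so Group 6 has 13 − 3 = 10 and Groups 7 and 8 have 9 each. N = 28, m = 3, df = 25. After the second vaccination, "the sample sizes of n=4, 5 for Groups 7-8 will be used to evaluate the immunogenicity post the 2nd vaccination", so there is only one pair. The checks assume normal data with a common variance. The documents give no AUC-MB means or variance, so the true shifts below are assumptions in SD units.

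**Multipliers at 25 df**
- As written: t(0.975; 25) = 2.060.
- Tukey-Kramer: q(0.95; 3 means, 25 df)/√2 = 2.491.
- Ratio: 2.491/2.060 = 1.209, so intervals about 21% wider.

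**Unconditional joint coverage.** The plan's figure is 95%. With equal group sizes, the joint coverage is P(q ≤ t√2), where q is the studentized range.
- Three regimens, 9/9/9 (24 df), exact: 0.881.
- Three regimens, 10/9/9 (25 df), simulated: 0.881 as written; 0.950 with Tukey-Kramer.
- Two regimens, at 10/9, 9/9 or 4/5: 0.950. One pair needs no adjustment (at 4/5, t on 7 df = 2.365, the same as Tukey).

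The stated 95% is therefore reproduced for two regimens and not for three.

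**Coverage of the sets actually reported.** The intervals appear only if F has p ≤ 0.05. Simulated at 10/9/9, given a significant F-test:

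| True shift (assumed) | Chance F is significant | As written | Tukey-Kramer |
|---|---|---|---|
| None | 0.05 | 0% | 9% |
| One arm +0.25 SD | 0.08 | 15% | 51% |
| One arm +0.5 SD | 0.17 | 58% | 79% |
| One arm +0.75 SD | 0.33 | 77% | 89% |
| One arm +1 SD | 0.54 | 85% | 93% |
| One arm +1.5 SD | 0.89 | 89% | 95.5% |
| One arm +2 SD | 0.99 | 88.5% | 95% |
| Arms at 0, 1, 2 SD | 0.96 | 89% | 95% |

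A significant F-test selects data sets with large observed differences. When the true differences are small, those are the sets most likely to miss the truth. While the gate stays, Tukey-Kramer does not guarantee 95% for the reported sets either.

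**Significance decisions.** Family-wise error of the F-gated LSD at 10/9/9 is 0.050 with no true differences, 0.047 with one arm at +1 SD and 0.050 at +2 SD. The tests hold their level.

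**The separate nominal set.** With the same S², these intervals are identical to the ones called simultaneous. If each pair uses its own pooled variance (16 or 17 df, t = 2.120 or 2.110), the nominal intervals are on average 2.0% to 2.4% wider than the simultaneous ones, which reverses the expected order.

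**Comparator.** Section 6.5.4.4 needs placebo recipients; Section 9.2.1 rules them out; Section 6.5.4.3 already uses a reference that exists, the pooled baseline samples. No arithmetic applies.

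**The case against.** The strongest reply is that almost nothing depends on this. The formula, the degrees of freedom and the LSD procedure are all spelled out, so a statistician would compute the right quantity whatever the adjective. That stands for the computation, but not for a reader who sees only the reported label.

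The section may also never be used. In version 2.0 the second primary endpoint is MSD binding (Section 3.1). Section 3.2 keeps only the mapping of FP-specific neutralizing activity, as an exploratory objective. Section 2.6 says that neutralization assays may be performed. Section 4 strikes the TZM-bl tier-2 breadth plan on which AUC-MB rests. No participant received a third vaccination, so three regimens passing a heterologous tier-2 screen may be unlikely. All of this stands and keeps the impact low.

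The status of the text is also uncertain. The supplied SAP covers safety only (SAP Section 2), and an immunogenicity SAP that was not supplied might settle both points. Section 6 presents itself as revised version 2.0 language, and Sections 6.5.4.3 and 6.5.4.4 show no strikethrough. Marks are incomplete elsewhere, however, as in Section 7.3.6, so some may be missing from the copy read.

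A reader might infer from 88% coverage that the pairwise tests carry a 12% false-positive rate. The documents do not support that: the tests are gated by the F-test, and with three groups this holds family-wise error at about 5% or below.

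**Conclusion.** Section 6.5.4.4 misstates the coverage of its intervals. With three regimens, unconditional joint coverage is about 88% against the stated 95%. Among sets reported after a significant F-test it ranges, for the non-zero shifts tried, from about 15% (one arm +0.25 SD) to about 89%. With two regimens the unconditional figure is 95% as labelled, and that includes any comparison after the second vaccination. These results assume normal data, a common variance and 10/9/9 evaluable participants; the conditional figures also rest on the assumed shifts.

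The max|B| selection rule cannot be run as written, because its comparator does not exist.

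A reader might also infer that the trial's main conclusions are at risk. They are not: neither primary objective uses these intervals, no F-gated decision changes, and the max|B| analysis is optional. This is a low-impact correction worth making if the section is kept.

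**What to change.** **Intervals, preferred.** Drop the word simultaneous and describe these as per-comparison (unadjusted) 95% LSD intervals, read after the F-test. Delete the separate nominal set, which is redundant when it uses the same S². This costs a few words and widens nothing.

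**Intervals, alternative.** If joint 95% intervals are wanted, use the Tukey-Kramer multiplier, in line with the Tukey rule in Section 6.5.4.1, and report them whether or not the F-test is significant. With three regimens they are about 21% wider (2.491 against 2.060 at 25 df). Changing the multiplier while keeping the gate is not enough: coverage of reported sets would still be about 79% at a shift of 0.5 SD.

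**Comparator.** In the max|B| rule, replace the placebo reference with the pooled baseline samples from Groups 6-8 used in Section 6.5.4.3. Any inference should allow for baseline and post-vaccination samples coming from the same participants.

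**Status.** Reconcile Sections 6.5.4.3 and 6.5.4.4 with Sections 3 and 4, either by marking them as exploratory and conditional on the assay being run, or by striking them. None of these changes needs new data.

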6.5.4.5 Analysis of binding antibody IgG/IgA responses measured by BAMA

The analysis of IgG, IgG3, and IgA binding antibody response to gp120, V1V2 and other antigens (V3, CD4i, gp41, and gp41 IDR) as measured by the BAMA assay will be evaluated and compared as described under the general approach. Scores measured the cross-reactivity among the gp120 and V1V2 will be derived. The details of the score derivations will be described in SAP. The derived scores will be evaluated and compared as described under the general approach.

6.5.4.6 Analysis of CD4+ and CD8+ T-cell response as measured by the ICS assay

The analysis of CD4+ and CD8+ T-cell response rates as measured by the ICS assay will be evaluated and compared as described under the general approach. For each T-cell subset, the positivity call for each peptide pool will include a multiple-comparison adjustment for the number of peptide pools used in the assay. In general, the Mixture Models for Single-cell Assays (MIMOSA) statistical framework (65) and/or the Fisher's exact test-based positivity criteria will be used. Details of the positivity criteria will be discussed in the SAP. The magnitude of marginal response will be analyzed as described for quantitative data in the general approach section. For each T-cell subset, graphs will be used to display the background-subtracted magnitudes for each participant by protein, treatment arm and timepoint. When 3 or more cytokines are being measured by the ICS assay, the polyfunctionality of ICS responses may also be analyzed as an exploratory endpoint. Besides descriptive plots of the magnitude of polyfunctional responses, the COMPASS (Combinatorial Polyfunctionality analysis of Antigen-Specific T-cell Subsets) statistical framework (66) may also be used to perform joint modelling of multiple T-cell subsets of different cytokine combinations. For example, the functionality score (FS) and the polyfunctionality score (PFS) may be used to summarize the multi parameter ICS responses.

6.5.5 Analyses prior to end of scheduled follow-up visits

Any analyses conducted prior to the end of the scheduled follow-up visits should not compromise the integrity of the trial in terms of participant retention or safety or immunogenicity endpoint assessments. In particular, early unblinded analyses by treatment assignment require careful consideration and should be made available on a need-to-know basis only.

6.5.5.1 Safety

During the course of the trial, unblinded analyses of safety data will be prepared approximately every 4 months for review by the safety monitoring board (SMB). During the course of the trial, unblinded analyses of safety data will be prepared approximately every 4 months during the main study for review by the SMB. Ad hoc safety reports may also be prepared for SMB review at the request of the HVTN 303 PSRT. The HVTN leadership must approve any other requests for unblinded safety data prior to the end of the scheduled follow-up visits.

6.5.5.2 Immunogenicity

An unblinded statistical analysis by treatment assignment of a primary immunogenicity endpoint may be performed when all participants have completed the corresponding primary immunogenicity visit and data are available for analysis from at least 80% of these participants. Similarly, an unblinded statistical analysis by treatment assignment of a secondary or exploratory

immunogenicity endpoint may be performed when all participants have completed the corresponding immunogenicity visit and data are available for analysis from at least 80% of these participants. However, such analyses for a secondary or exploratory immunogenicity endpoint will only take place after at least 1 of the primary immunogenicity endpoints of the same class (humoral, cell-mediated, innate or mucosal) or, if no primary endpoint of the same class, at least 1 of the primary immunogenicity endpoints reaches the aforementioned threshold. The Laboratory Program will review the analysis report prior to distribution to the protocol chairs, DAIDS, vaccine developer, and other key HVTN members and investigators. Distribution of reports will be limited to those with a need to know for the purpose of informing future trial-related decisions. The HVTN leadership must approve any other requests for HVTN immunogenicity analyses prior to the end of the scheduled follow-up visits.

7 Study product preparation, storage, and administration

On January 13, 2023, a protocol memo was distributed informing the clinical research sites that all vaccinations in HVTN 303 were permanently discontinued. The vaccination that did not take place due to this has been marked with ~~strikethrough~~.

CRS pharmacists should consult the Pharmacy Guidelines and Instructions for DAIDS Clinical Trials Networks for standard pharmacy operations. The protocol schema is shown in [Table 1-1](#). See the Investigator's Brochures (IBs) for further information about study products.

7.1 Vaccine Regimen

The schedule of study product administration is shown in [Section 1.5](#) and additional information is given below.

Part A

Group 1

Treatment 1 (T1):

25 mcg FP Conjugate Vaccine (FP8v1-rTTHC; VRC-HIVVCP0108-00-VP) + 20% dose/volume (d/v) Adjuplex, to be administered as 0.8 mL, divided into 2 syringes (0.4 mL each), intramuscularly at Week 0.

Group 2

Treatment 2 (T2):

200 mcg FP conjugate vaccine (FP8v1-rTTHC; VRC-HIVVCP0108-00-VP) + 20% dose/volume (d/v) Adjuplex, to be administered as 0.8 mL, divided into 2 syringes (0.4 mL each), intramuscularly at Week 0.

Group 3

Treatment 3 (T3):

100 mcg Trimer 6931 (HIV-1 Trimer 6931 Vaccine; VRC-HIVRGP0106-00-VP) + 20% dose/volume (d/v) Adjuplex, to be administered as 0.8 mL, divided into 2 syringes (0.4 mL each), intramuscularly at Week 0.

Group 4

Treatment 4 (T4):

200 mcg Trimer 6931 (HIV-1 Trimer 6931 Vaccine; VRC-HIVRGP0106-00-VP) + 20% dose/volume (d/v) Adjuplex, to be administered as 0.8 mL, divided into 2 syringes (0.4 mL), intramuscularly at Week 0.

Group 5

Treatment 5 (T5):

200 mcg Trimer 4571 (HIV-1 Trimer 4571 Vaccine; VRC-HIVRGP096-00-VP) + 20% dose/volume (d/v) Adjuplex, to be administered as 0.8 mL, divided into 2 syringes (0.4 mL each), intramuscularly at Week 0.

Part B

Group 6

Treatment 6 (T6):

200 mcg Trimer 4571 + 20% dose/volume (d/v) Adjuplex, to be administered as 0.8 mL, divided into 2 syringes (0.4 mL each), intramuscularly at Weeks 0 and 12.

~~200 meg Trimer 6931 + 20% dose/volume (d/v) Adjuplex, to be administered as 0.8 mL, divided into 2 syringes (0.4 mL each), intramuscularly at Week 24.~~

~~100 meg Trimer 4571 + 100 meg Trimer 6931 + 20% dose/volume (d/v) Adjuplex, to be administered as 0.8 mL, divided into 2 syringes (0.4 mL each), at Weeks 36 and 48.~~

Group 7

Treatment 7 (T7):

200 mcg FP conjugate vaccine + 20% dose/volume (d/v) Adjuplex, to be administered as 0.8 mL, divided into 2 syringes (0.4 mL each), at Weeks 0 and 4 and 8.

~~200 meg Trimer 4571 + 20% dose/volume (d/v) Adjuplex, to be administered as 0.8 mL, divided into 2 syringes (0.4 mL each), intramuscularly at Weeks 12 and 24.~~

~~200 meg Trimer 6931 + 20% dose/volume (d/v) Adjuplex, to be administered as 0.8 mL, divided into 2 syringes (0.4 mL each), intramuscularly at Week 36.~~

~~100 mcg Trimer 4571 + 100 mcg Trimer 6931 + 20% dose/volume (d/v)
Adjuplex, to be administered as 0.8 mL, divided into 2 syringes (0.4 mL each), at
Week 48.~~

Group 8

Treatment 8 (T8):

200 mcg FP conjugate vaccine + 200 mcg Trimer 4571 + 20% dose/volume (d/v)
Adjuplex, to be administered as 0.8 mL, divided into 2 syringes (0.4 mL each), at
Weeks 0 and 4 and 8.

~~200 mcg Trimer 6931 + 20% dose/volume (d/v) Adjuplex, to be administered as
0.8 mL, divided into 2 syringes (0.4 mL each), intramuscularly at Week 20.~~

~~100 mcg Trimer 4571 + 100 mcg Trimer 6931 + 20% dose/volume (d/v)
Adjuplex, to be administered as 0.8 mL, divided into 2 syringes (0.4 mL each),
intramuscularly at Weeks 32 and 44.~~

